## Group B – Biopsy Arm – Schedule and Planned Activities

	Screening (Visit 1)	Treatment (Visit 2)	Follow-Up Phone Call	Follow-Up Biopsy	Follow-Up Biopsy
Visit Number	1	2	3	4, 5	6
Study Day #	0	0	2 (<math>\pm 1</math>)	4 (<math>\pm 1</math>), 12 (<math>\pm 2</math>)	19 - 90
Screening Activities	X				
Pregnancy Test	X	X			
Photographs		X		X	X
Biopsy		X	X	X	X
Adverse Event Assessment		X	X	X	X

## 6.2.1 UNSCHEDULED VISIT

Any unscheduled visit or examination should be documented in the participant's medical record and adverse event form (if applicable) stating the reason for the visit and any actions taken. The Sponsor should be notified of the unscheduled visit.

## 6.3 STUDY TREATMENT

Participants in Group A, the clinical treatment arm, will receive up to 5 treatments at the investigator's discretion using the Mosaic Ultra Treatment Parameter Guidelines as a starting point for the treatment parameters. Treatments will occur 2-6 weeks apart depending on the clinical indication being treated. Participants in Group B, the biopsy arm, will only receive one treatment with pre-determined parameters in a discrete area of the body (such as abdomen, buttocks, back).

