## PROTOCOL SYNOPSIS

Protocol Number:	LMI22001
Protocol Title:	Safety and Efficacy of the Mosaic Ultra Device
Investigational Devices:	Mosaic Ultra
Development Phase:	Pilot
Study Objective:	Evaluate the Safety and Efficacy of the Mosaic Ultra 1550nm system for the treatment of skin tone and texture, facial rejuvenation, photoaging, wrinkles, scars, stretch marks, acne vulgaris and hair loss.
Brief Study Overview:	
Prospective, Multi-Site, Non-Randomized study of up to 210 participants in two treatment groups
 
 
• Group A: Clinical Treatment Arm (n=180)
 
• Group B: Biopsy Arm (n=30)
 
 
Subject's in Group A will be treated with the device with the recommended parameters based on pre-clinical testing and similar device parameters. Subjects will receive up to 5 treatments and then attend follow-ups 30 and 90-days post treatment. Subject's may be asked to participate in an optional biopsy portion of this arm
 
Subject's in group B will be treated at pre-determined parameters based on regulatory body requirements. Subjects will return up to 3 months post treatment. 5 Biopsies will be collected prior to treatment and throughout the follow-up periods.

Number of Sites Enrolling Participants:	3 sites located in the United States
Sample Size:	N = up to 210 treated participants
Participant Population:	Healthy adults, male and female, at least 18 years old who meet the inclusion and exclusion criteria.
Inclusion Criteria:	
 
• Non-smoking, Male or Female
 
• Age 18 – 60 years old
 
• Understands and accepts the obligation not to undergo any other procedures in the areas to be treated.
 
• Participants who are willing and able to comply with all study participation requirements including returning for follow-up visits and abstaining from exclusionary procedures for the duration of the study.
 
• OPTIONAL - Participants who are willing to undergo biopsies.
 

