### 6.2 STUDY SCHEDULE

Table 5: Study Schedule

Group A – Clinical Treatment Arm – Schedule and Planned Activities

	Screening	Treatment	Post Treatment Follow-Up (optional) 1-7days post Tx	Follow-Up 30-day post final TX	Follow-Up 90-day post final TX
Visit Number	1	2, 4, 6, 8, 10	3, 5, 7, 9, 11	12	13
Study Day #	0	0 – 140	1-147	170 (±7)	230 (±14)
Screening Activities	X				
Pregnancy Test	X	X			
Photographs		X	X	X	X
Device Treatment		X			
Biopsy (optional)		X	X	X	X
Adverse Event Assessment		X	X	X	X
Subject Evaluations				X	X
Physician Evaluation				X	X

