### 6.3.6 ELECTIVE SKIN BIOPSY

Some study-site locations may offer an elective skin biopsy for histological evaluations. The biopsy is considered a safe, low-risk procedure.

The biopsy procedure will involve collecting a small sample of skin from the participant in a discreet location. The punch biopsy, a tool that is usually circular at the extraction site, removes a small, round sample of the epidermis, dermis, and superficial fat (while leaving the extracted layers intact).

Prior to biopsy, participant skin will be cleaned and dried by the treating clinician. The punch instrument is pressed vertically into the skin and then rotated clockwise and counterclockwise between the fingertips. A small “give” can be felt as the device cuts through the epidermis and dermis, down to the superficial layer of subcutaneous fat. The punch biopsy tool is designed to collect tissue very quickly (to reduce pain) and is also designed to reduce the risks of bleeding through precision. However, some temporary pain and minor bleeding can occur at the biopsy site. The biopsy site will be covered with a bandage. There is a small risk of infection and participants must commit to taking care of biopsy site. Participants will be advised to regularly clean the biopsy site with mild soap and water, and to keep it bandaged (a simple bandaid is often enough) until it is fully healed (approximately one month).

For patients participating in the Group B of the study, the intended treatment area of the subject will be marked and photographed prior to treatment and a control biopsy will be taken. The first biopsy (Day 0, control) will be collected at this time. A normal treatment will be then be conducted using pre-determined laser parameters. Subject will then have a biopsy taken immediately post treatment from the treated area.

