#### **6.4 FOLLOW-UP VISITS**

Post-treatment follow-ups may occur up to 7 days post-treatment. These follow-ups are optional and may be conducted in-phone, over email, or in-person as determined by the clinician. If an optional post-treatment follow-up is determined necessary by the clinician the subject will be notified before the end of their treatment visit and the visit will be scheduled at that time. Adverse events will be evaluated at this visit. If subject has elected to participate in the biopsy portion of the study then a biopsy may also be collected at this visit.

In-person follow up visits will occur  $30\pm 7$  and  $90\pm 14$  days post final treatment. Adverse events will be assessed at these visits. Subjects will be asked to rate their satisfaction (Table 3) with their overall results as well as grade their improvement on the CGAIS (Table 4).

Subjects in Group B will then return 3 and 14 days post treatment to have an additional biopsy collected from the treated area. Subject's will then return for a final follow-up for biopsy collection between 19 and 90 days post treatment. Photos will be taken at all visits to ensure proper collection of biopsies as well as to capture the skin response.

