## 9. STATISTICAL ANALYSIS

### 9.1 STATISTICAL AND ANALYTICAL PLANS

The primary analysis of efficacy will be by study group and will be based on the evaluable treated participants; hence, only those participants who received complete study treatments and completed a 30-day/90-day follow-up visit post-the-final-treatment-visit, and who have evaluable post-treatment images, will be included in the analysis. Analyses of safety will include all participants who received (complete or incomplete) study treatment.

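### Table 5's fixed study days match the final-treatment follow-up rule only when the last Group A treatment falls near day 140; the Group B biopsy schedule also conflicts with the text

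*Combined protocol and SAP*

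**What the plan says.** **Group A.** Section 6.3 permits up to five treatments, the number being left to the investigator, and states: "Treatments will occur 2-6 weeks apart depending on the clinical indication being treated". Table 5 (Section 6.2) gives study days 0-140 for treatment, 1-147 for the optional visits after treatment, 170 (±7) for the first follow-up and 230 (±14) for the second. The heading over the last column reads "Follow-Up 90-day post final TX", and the preceding column has the matching 30-day heading. Section 6.4 sets the in-person visits at 30±7 and 90±14 "days post final treatment. Adverse events will be assessed at these visits". Section 9.1 limits the primary efficacy analysis to participants who, among other conditions, "completed a 30-day/90-day follow-up visit post-the-final-treatment-visit". The synopsis bases the Group A primary endpoint on the 3-month image.

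**Group B.** Table 5 gives early biopsies at days 4 (±1) and 12 (±2). Section 6.4 says: "Subjects in Group B will then return 3 and 14 days post treatment to have an additional biopsy collected from the treated area". It gives no window. Both places put the final biopsy at days 19-90. Table 5 also marks a biopsy at Visit 3, day 2 (±1), whose column is headed "Follow-Up Phone Call". The synopsis gives the total: "5 Biopsies will be collected prior to treatment and throughout the follow-up periods".

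**The concern.** Table 5 carries two timing rules for the same Group A visits. The headings float with the last treatment, while the Study Day row is fixed and has its own windows. Section 6.3 lets the last treatment move by months, so the two cannot agree in general, and no rule says which one governs.

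The visit at stake is the one that supplies the primary-endpoint image. A site that books by the Study Day row may photograph participants at very different intervals after treatment. A visit that is on time under Section 6.4 can also be out of window under Table 5, which matters when deviations are judged for the per-protocol set in Section 9.2. The loss-to-follow-up rule in Section 5.3 (recruitment and retention) counts six weeks from the last follow-up target. For a participant treated once, that is day 90+42 = 132 by one rule and day 230+42 = 272 by the other.

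In Group B, histology is the primary endpoint, and sites could work to different early biopsy days.

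**Working it through.** **Inputs.** At most 5 treatments, so at most 4 gaps, each 14-42 days (Section 6.3). Treatment days 0-140; follow-up days 170 (±7) and 230 (±14) (Table 5). Follow-up at 30±7 and 90±14 days after the final treatment (Section 6.4). The first treatment is taken as day 0, and D is the day of the last treatment.

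**Where the table's figures come from.** 140+7 = 147, 140+30 = 170 and 140+90 = 230. The row is therefore built on D = 140, that is, five treatments averaging 140/4 = 35 days apart.

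**Range of D for five treatments.** Shortest 4×14 = 56; longest 4×42 = 168. The longest course runs 168−140 = 28 days past the table's limit, and its last optional visit could fall as late as 168+7 = 175, not 147.

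**When one visit can satisfy both rules.**
- 30-day visit: D+23 to D+37 must meet 163-177. This needs D ≥ 163−37 = 126 and D ≤ 177−23 = 154.
- 90-day visit: D+76 to D+104 must meet 216-244. This needs D ≥ 216−104 = 112 and D ≤ 244−76 = 168.

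A stricter test asks when the nominal day itself is in window. Day 170 qualifies only for D = 133-147, and day 230 only for D = 126-154.

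**Which courses qualify for the 90-day visit.** The latest possible D for 1, 2, 3, 4 and 5 treatments is 0, 42, 84, 126 and 168.
- Three or fewer: the latest D is 84, below 112, so the windows never overlap.
- Four: overlap only for D = 112-126, an average gap of 112/3 = 37.3 to 126/3 = 42 days.
- Five: overlap only for D = 112-168, an average gap of 112/4 = 28 to 168/4 = 42 days.

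**Five equally spaced treatments:**

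| Gap | D | 90-day window (D+76 to D+104) | Shared with 216-244 | 230−D |
|---|---|---|---|---|
| 2 weeks | 56 | 132-160 | none | 174 |
| 3 weeks | 84 | 160-188 | none | 146 |
| 4 weeks | 112 | 188-216 | day 216 only | 118 |
| 5 weeks | 140 | 216-244 | all | 90 |
| 6 weeks | 168 | 244-272 | day 244 only | 62 |

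At 6 weeks the 30-day windows do not meet at all: 191-205 against 163-177.

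**Group B days.** The Table 5 windows are 3-5 and 10-14. The Section 6.4 days, 3 and 14, sit on their edges. The targets differ by 1 day (4 against 3) and 2 days (12 against 14), but both can be met.

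**Group B count.** Section 6.3.6 describes a day 0 control biopsy and then says: "Subject will then have a biopsy taken immediately post treatment from the treated area". With two early biopsies and one final, 1+1+2+1 = 5, which is the synopsis total. A biopsy at Visit 3 would make 6. The photograph row is blank for that visit, although Section 6.4 ties photographs to biopsy collection.

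**The case against.** The strongest reply is that the Study Day row only illustrates a full course. It numbers five treatment visits, gives treatment as a range, and agrees exactly with its headings when the last treatment is on day 140. The headings, Section 6.4 and Section 9.1 all point to the final treatment, so a careful site will book from that date, and central monitoring reviews compliance and photographs. The 28-day shortfall arises only when five treatments average more than 35 days apart. How often that would happen is unknown, because the treatment guidelines in Appendix B are not included. The Group B days can be reconciled, and the phone-call mark is an obvious slip or possibly an artefact of reading the table.

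Much of this stands. The intended anchor can be recovered, the harm arises only if a site follows the row, and the Group B points are minor. The table's blank photograph cell at Visit 3 makes a reading error less likely, though it cannot be excluded.

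The reply does not clear the row itself. Nothing labels it illustrative, and it has its own tolerances. As a maximum it is 28 days short of what Section 6.3 permits.

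**Conclusion.** The concern holds. The Group A Study Day row is wrong as a general schedule. Its day 140 limit excludes five treatments at the permitted 6-week spacing, and its follow-up days are compatible with the final-treatment rule only for a last treatment on days 126-154 (30-day visit) or 112-168 (90-day visit). Across five-treatment courses with equal gaps of 2 to 6 weeks, study day 230 ranges from 174 to 62 days after the last treatment.

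These figures assume that the first treatment is on day 0 and that every spacing in Section 6.3 can occur with any number of treatments. The effect on the primary image depends on a site using the row instead of the headings, and the documents do not show how likely that is.

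The Group B differences of 1 and 2 days are real but can be accommodated within the table's windows. The phone-call biopsy mark is most likely stray. None of this invalidates the trial, but it should be corrected because it concerns the timing of primary-endpoint data.

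**What to change.** - In the Group A part of Table 5, set treatment to days 0-168 and the optional visits to days 1-175. Alternatively, limit the spacing in Section 6.3 so that five treatments end by day 140.
- Replace study days 170 (±7) and 230 (±14) with final treatment +30 (±7) and final treatment +90 (±14). Derive analysis windows from each participant's actual final treatment date.
- State one set of Group B early biopsy days, with windows, in both Table 5 and Section 6.4.
- Remove the biopsy mark from the Visit 3 phone call.

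The sponsor decides which spacing and which biopsy days apply. The cost is a corrected table and matching wording in Section 6.3 or 6.4 through a protocol amendment, with no extra visits, participants or procedures.

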## 6.3.1 PRE-TREATMENT MEDICATIONS

No pre-treatment medication prior to study treatment.

## 6.3.2 PARTICIPANT PREPARATION FOR STUDY TREATMENT

The investigator, sub-investigator, or delegated clinician will first identify the skin areas to which treatment/exposure is to be performed. Treatment records will be maintained in accordance with this protocol. Skin in treatment area should be cleansed with mild cleaner. No lotion, make-up, perfume, powder, or oil should be present on the area to be treated. Area will be fully cleansed prior to treatment. Test spots will be done as per the Mosaic Ultra guidelines to ensure the device settings are appropriate for the skin type (with adjustments to be made to the device settings as determined appropriate from observation of the reaction of the test spots).

## 6.3.3 STUDY TREATMENT

All study treatments will be performed by the investigator, sub-investigator, or delegated clinician (ie, study exposure clinician as designated by the principal investigator). Participants will receive up to 5 treatments at the investigator's discretion using the Mosaic Ultra Treatment Parameter Guidelines as a starting point for the treatment parameters. The participants will be monitored during the exposure. The participant's pain levels will be monitored using a standard pain scale assessment (0-10). The average pain score will be recorded. Participants in Group B, the biopsy arm, will receive treatment in a discrete area such as the back, abdomen, or buttocks.

### 6.3.4 ACUTE RESPONSES

For all exposures, acute responses (eg, erythema or edema) will be observed by the study exposure clinician and recorded after exposure. If any Serious Adverse Events (SAE) are noted, an SAE Form should be completed.

### 6.3.5 POST-TREATMENT CARE

Participants will be advised:

- Do not use any scrubbing product for one week after treatment.
- Do not use functional cosmetics (eg, retinol, AHA) for 2 days.
- Avoid saunas for at least one week.
- Do not use cosmetic products (toner, lotion) containing alcohol. They may cause skin irritation. Use a mild moisturizer.
- Apply sun block cream (SPF 30, PA++) everyday, to prevent PIH. It is advisable to wear a hat and take an umbrella when going outside for 30 days after the procedure.
- Skin Dryness are normal reactions associated with the thermal effect, so please apply moisturizing cream frequently.

For subjects in Group B, post-biopsy instruction will be provided to the participant. The participant will be instructed to not fully submerge the biopsy site in water. The bandage or coverings for the biopsy site should be changed on a daily basis and should also be changed if it becomes wet or damp. The subject will also be told that once a scab or new skin begins to grow over the area and that the bleeding from the biopsy site has stopped they can discontinue the wound treatment regimen and remove the bandage.

Other post-treatment procedures will be considered and used as deemed by a clinician to be standard and reasonable care. Participants will be instructed that blistering, bleeding, oozing, strong pain, excessive swelling persisting for more than 48 hours, or signs of infection (eg, itching; pus; drainage; fever; chills) are cause for immediate concern.

There is a risk of an allergic reaction to the anesthetic or oral medication used in treatment and/or the biopsy. An allergic reaction to the anesthetic may cause: hives, itching, swelling, faintness, low blood pressure, difficulty breathing, and life-threatening shock. In the event of the aforementioned infection or allergic reaction scenarios, immediate emergencies (medically unstable) must be triaged in emergency care.

If the aforementioned side-effects are not an immediate emergency (medically stable), participants should contact the investigator and/or his designee, to be evaluated and potentially treated at no cost to the participant. An unscheduled visit will be arranged so that the Investigator can clinically evaluate and photograph these findings.

### 6.3.6 ELECTIVE SKIN BIOPSY

Some study-site locations may offer an elective skin biopsy for histological evaluations. The biopsy is considered a safe, low-risk procedure.

The biopsy procedure will involve collecting a small sample of skin from the participant in a discreet location. The punch biopsy, a tool that is usually circular at the extraction site, removes a small, round sample of the epidermis, dermis, and superficial fat (while leaving the extracted layers intact).

Prior to biopsy, participant skin will be cleaned and dried by the treating clinician. The punch instrument is pressed vertically into the skin and then rotated clockwise and counterclockwise between the fingertips. A small “give” can be felt as the device cuts through the epidermis and dermis, down to the superficial layer of subcutaneous fat. The punch biopsy tool is designed to collect tissue very quickly (to reduce pain) and is also designed to reduce the risks of bleeding through precision. However, some temporary pain and minor bleeding can occur at the biopsy site. The biopsy site will be covered with a bandage. There is a small risk of infection and participants must commit to taking care of biopsy site. Participants will be advised to regularly clean the biopsy site with mild soap and water, and to keep it bandaged (a simple bandaid is often enough) until it is fully healed (approximately one month).

For patients participating in the Group B of the study, the intended treatment area of the subject will be marked and photographed prior to treatment and a control biopsy will be taken. The first biopsy (Day 0, control) will be collected at this time. A normal treatment will be then be conducted using pre-determined laser parameters. Subject will then have a biopsy taken immediately post treatment from the treated area.

#### **6.4 FOLLOW-UP VISITS**

Post-treatment follow-ups may occur up to 7 days post-treatment. These follow-ups are optional and may be conducted in-phone, over email, or in-person as determined by the clinician. If an optional post-treatment follow-up is determined necessary by the clinician the subject will be notified before the end of their treatment visit and the visit will be scheduled at that time. Adverse events will be evaluated at this visit. If subject has elected to participate in the biopsy portion of the study then a biopsy may also be collected at this visit.

In-person follow up visits will occur  $30\pm 7$  and  $90\pm 14$  days post final treatment. Adverse events will be assessed at these visits. Subjects will be asked to rate their satisfaction (Table 3) with their overall results as well as grade their improvement on the CGAIS (Table 4).

Subjects in Group B will then return 3 and 14 days post treatment to have an additional biopsy collected from the treated area. Subject's will then return for a final follow-up for biopsy collection between 19 and 90 days post treatment. Photos will be taken at all visits to ensure proper collection of biopsies as well as to capture the skin response.

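### Sections 7.3 and 7.4.1 give opposite rules for an adverse event still open at the final visit, which is also when the last punch biopsy is taken

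*Combined protocol and SAP*

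**What the plan says.** **Timing of the last biopsy.** Section 6.4 has Group B participants "return for a final follow-up for biopsy collection between 19 and 90 days post treatment". In Table 5 (Section 6.2) this is Visit 6, the last column for Group B, with both a biopsy and an AE assessment marked and nothing scheduled afterwards. For Group A, Table 5 allows an optional biopsy at Visit 13, 90 days after the final treatment, which is also the last column.

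**Follow-up of open events.** Section 7.3 requires every unresolved event to be followed by telephone, e-mail or visit at intervals of 7 days or less, until it resolves or stabilizes. Section 7.4.1 first says that events are followed to the last visit or to resolution. It then says flatly that AE follow-up stops at the final visit.

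**Recording of new events.** Section 7.3 works by start date. Non-serious events count if they begin up to 7 days after the last day of participation, and serious events up to 30 days.

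**Biopsy wounds.** Section 6.3.6 acknowledges a small infection risk and tells participants to keep the site bandaged "until it is fully healed (approximately one month"). Section 6.3.5 lets Group B participants stop wound care "once a scab or new skin begins to grow over the area and that the bleeding from the biopsy site has stopped".

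**Self-report.** Section 6.3.5 warns participants about "blistering, bleeding, oozing, strong pain, excessive swelling persisting for more than 48 hours, or signs of infection (eg, itching; pus; drainage; fever; chills") and asks medically stable participants to contact the investigator. It adds: "An unscheduled visit will be arranged so that the Investigator can clinically evaluate and photograph these findings". Section 6.2.1 has such visits documented in the "medical record and adverse event form (if applicable").

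**The concern.** A coordinator with an unresolved AE at the final visit finds two instructions that cannot both be followed: keep contacting the participant, or stop. Sites could act differently on identical events, and whichever follows 7.4.1 would leave the outcome unknown.

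The conflict is study-wide, but it bears most on biopsied participants because the schedule makes a fresh wound at the very visit after which 7.4.1 stops follow-up. AE assessment is a listed secondary endpoint (Section 4.3.2), and an acceptable AE profile is a Group A success criterion (Section 4.4). The biopsy wound is also a risk that the study itself creates, so follow-up to resolution is a participant-safety matter as well as a data matter.

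The second, smaller issue is that the 7-day window for new non-serious events is shorter than the healing time the protocol gives for the wound.

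**Working it through.** The plan has no figure of its own to reproduce. The check is a comparison of the two rules, followed by day counts.

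**1. The two rules side by side**

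| Situation | Section 7.3 | Section 7.4.1 |
|---|---|---|
| AE open at the final visit | Contact at least every 7 days to resolution or stabilization | No follow-up after that visit (its preceding sentence also allows follow-up to resolution) |
| Non-serious AE starting within 7 days after exit | Recorded and followed for outcome | No follow-up |

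The second row matters for the last biopsy, since most problems at a site sampled at the final visit would begin after the participant has left. The first row matters for earlier sites, such as one sampled around Day 12 with Visit 6 on Day 19.

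**2. Recording window for the last Group B biopsy**

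Assumptions: the last day of participation is the final visit, and one month is 30 days. With the last biopsy on Day *d*, from 19 to 90:

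- Non-serious window closes at *d* + 7: Day 26 to Day 97.
- Serious window closes at *d* + 30: Day 49 to Day 120.
- Healing by the Section 6.3.6 figure ends at about *d* + 30: Day 49 to Day 120.

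Days of healing outside the non-serious window: 30 − 7 = 23. If sites close sooner (assumed 21 or 14 days), 21 − 7 = 14 or 14 − 7 = 7. The serious window covers the whole period.

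**3. The earlier Group B biopsies, if exit is on Day 19**

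Recording then ends on Day 26. Cover for each site is 26 minus the biopsy day:

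- Two Day 0 sites: 26 days.
- Day 3 to 5 site: 21 to 23 days.
- Day 10 to 14 site: 12 to 16 days.

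All fall short of 30 days, so one site per participant is a minimum. With later exit the shortfall disappears for these four: a Day 14 site has 30 days of recording if exit is on Day 37 or later (37 + 7 − 14 = 30). The last site always has 7.

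**4. Load of an optional check at 30 days**

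- Group B: up to 30 contacts. At an assumed 5 to 15 minutes each, 30 × 5 = 150 minutes (2.5 hours) to 30 × 15 = 450 minutes (7.5 hours).
- Latest Group B contact: Day 90 + 30 = Day 120.
- Group A on the full five-treatment schedule: Visit 13 at nominal Day 230, contact at about Day 260. The number biopsied at Visit 13 is not given; the bounds are 0 and 180.

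**The case against.** **The two sections can be reconciled.** One could read 7.3 as governing events during the study and 7.4.1 as setting the end point. This does not work: 7.3 itself takes in events that begin after the last day of participation and asks for their outcome. Section 7.4.1 is also unclear within itself, because its preceding sentence allows follow-up to resolution.

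**The 7-day window is a reasonable choice.** This largely stands. The protocol regards the biopsy as low-risk, and serious events, including those needing intervention to prevent permanent damage, are recorded to 30 days. Participants are told what to look for, and an unscheduled visit is available with no stated time limit. An event that starts within 7 days but is reported later is still recordable. What remains is the late-starting, non-serious event. Sections 6.3.5 and 6.2.1 provide care and documentation for it, but they do not extend the 7.3 window.

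**The day counts overstate the problem.** A reader might infer from 23 of 30 days that about three-quarters of biopsy-site harm goes unrecorded, or that the safety conclusions are unsound. The documents do not support that. The one-month figure is bandaging advice, not a period of constant risk, and no onset distribution or event rate is given. Section 6.3.5 also contemplates earlier closure in Group B. The other four Group B sites are watched longer than the fifth, and late minor events at a biopsy site say little about the laser.

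**A call at 30 days does little.** It is prompted self-report, comes late for infection, and cannot alone tell slow healing from normal healing. That is why it is optional here.

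**Conclusion.** The conflict between 7.3 and 7.4.1 is established from the text and should be corrected. It applies to any AE open at exit, in both groups and at every site, and bears most on participants biopsied at their final visit: up to 30 in Group B and an unstated number in Group A.

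The 7-day recording window is a minor gap, worth closing only because the same amendment can do it. The number of events gained is unknown and probably small. Neither issue affects the blinded image assessment or the histology endpoint, and Group B success rests on histology alone.

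**What to change.** 1. Delete or amend the closing sentence of Section 7.4.1 so that events open at the final visit are followed to resolution or stabilization as in Section 7.3.
2. In Section 7.3, record non-serious biopsy-site events that start up to 30 days after the last biopsy. This matches the serious-event window and, counted from the last biopsy, covers the earlier sites too. Section 2.3.1.1 already uses 30 days, though for a different case (treatment stopped for intolerance).
3. Repeat the Section 6.3.5 self-report instruction at the last visit, since early infection will continue to be found that way.
4. Optionally, add one telephone or e-mail contact about 30 days after the last biopsy, for Group B and for Group A participants biopsied at Visit 13. Ask about the Section 6.3.5 signs, their start dates, and whether the site has closed. Continue following anything still open.

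**Cost.** Items 1 to 3 need an IRB-approved amendment (Sections 11.2 and 13.2) and little else beyond following the open events. Item 4 adds the Group B staff time worked out above, plus one contact per Group A participant biopsied at Visit 13. Group B already has a call with AE assessment at Visit 3 ("Follow-Up Phone Call"), so no new type of contact is needed. Group B contacts would end well before a full-schedule Group A participant exits, but a Visit 13 biopsy could put that participant's safety close-out back by up to about one month.
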